10.2. Data Safety Monitoring Board

The DSMB will be composed of independent experts in vaccines, infectious diseases, pediatrics and biostatistics. There will be no formal meetings of the DSMB however, they would convene on an as-needed basis. If the PSRT elects to implement a study pause, the study team will pause the study for randomization and vaccination purposes, until the DSMB approves lifting the pause based on unblinded review of all safety data accrued during the trial. DSMB reviews will indicate whether or not safety concerns were identified, and whether the trial should continue without change, be modified, or be terminated. The Sponsor will carefully consider the DSMB recommendations. If the Sponsor does not agree with these recommendations, a meeting will be held between the Sponsor, PI and DSMB to reach consensus on the appropriate action(s) to take in regard to the trial. However, if attempts to reach consensus fail, the Sponsor's opinion will prevail. In such situations, the Sponsor will inform the regulatory authorities, The Gambia Government/MRC Joint ethics committee, LSHTM Research Ethics Committee and WIRB of the DSMB findings, the Sponsor's perspective, and any changes to the trial.

The PSRT, PI or PATH Clinical Lead may also seek additional guidance from the DSMB as dictated by the occurrence of certain events that do not warrant a study pause.

10.3. Protocol Deviation and Protocol Violation

A protocol deviation is any noncompliance with the clinical trial protocol, GCP, or site SOP/SSP requirements. The noncompliance may be either on the part of the subject or the site team/PI.

A protocol violation is a significant departure from processes or procedures required by the protocol. Violations often result in data that are not deemed evaluable for a *per-protocol* analysis, and may require that the subject(s) who violates the protocol be discontinued from the study.⁴⁰

When appropriate, corrective actions and preventive actions (CAPAs) will be developed by the site to address protocol violations and deviations, and will be implemented promptly. These practices will be consistent with ICH E6 (R2) Guidelines.

11. DATA MANAGEMENT

The Sponsor-designated CRO's study monitors will visit the site at regular intervals (including field sites) as per the monitoring plan and perform pre-agreed source data verification of the data recorded in the paper CRF against the source documents available at the site. In addition, missing data forms and fields will be queried by daily electronic edit checks or through manual edits of the data by the data management team. Study monitors will closely evaluate pre-screening data, inclusion/exclusion criteria, informed consents, data entry timeliness, and visit dates and windows at each field site to ensure integrity of the study is maintained.

Any data discrepancies generated by the system will be flagged in the OpenClinica database system for the PI to provide a satisfactory resolution within the OpenClinica database system. The data management team will review all the data discrepancy responses by the site to ensure the correctness of data. The AEs will be coded using MedDRA dictionary version 21.0 or later and the concomitant medications will be coded using standard nomenclature. After completion of data coding and resolution of all the queries in the database pertaining to subject visits through completion of Visit 4 by the last subject, the database will be declared to be accurate and statistical analysis of secondary immunogenicity objectives, and safety and tolerability, through V4 will take place. A final database lock will occur after completion of data coding and resolution of all the queries in the database following completion of Visit 6 by the last subject (LSLV).

11.1. Case Report Form Development and Completion

Based on the final protocol of the study, a comprehensive set of paper CRFs will be prepared to capture all the relevant data required for analysis and reporting. This study will utilize the OpenClinica system such that the entire study data can be maintained in a secure electronic system. No written or electronic data recorded prior to the study will be included in the paper CRFs or OpenClinica system respectively.

All study data will be collected by the clinical study staff using designated source documents, wherever applicable, and will be entered in the appropriate CRFs and OpenClinica system in an anonymized form. In some cases, the CRF will be the source document. The study database will identify study subjects only by unique study ID numbers through screening (screening number) and randomization assignments (randomization ID) and will not contain any identifying information such as name, address or personal contact information, or any other national ID number. CRFs will be reviewed by the clinical team who are responsible for ensuring that they are accurate and complete.

The data management activities will be performed as per the CRO's SOPs. The appropriately trained site personnel will ensure double data entry of the study data recorded on the CRFs into the OpenClinica system. To ensure that data are entered in a timely fashion so as to monitor safety of the study, it is expected that the site will maintain data entry with a minimal expectation of 3 business days from subject clinic visit or last home visit. The study monitor plan will include assessments of data entry timeliness.

The study site will maintain the source documents for each study subject. The source documents and other supporting documents will be kept in a secure location. Source documentation will be available for review by the study monitor to ensure that the source data are consistent with the CRFs.

11.2. Record Archival

11.2.1. Archiving Data at Study Site

The study site will maintain appropriate medical and research records for this trial, in compliance with ICH-GCP, regulatory, sponsoring organization and institutional requirements for the protection of confidentiality of subjects. The site will permit authorized representatives of the Sponsor and regulatory agencies to examine (and when required by applicable law, to copy) clinical records for the purposes of quality assurance reviews, audits, and evaluation of the study safety and progress. The final database will be locked and transferred to the Sponsor for long-term storage.

11.2.2. Data Storage and Archival

The PI will maintain an Investigator Site File, which will be used to file the IB, protocol, vaccine accountability records, correspondence with the EC/IRB, Sponsor, CRO, and other study-related documents. The PI will maintain, and store securely, complete, accurate and current study records throughout the study.

As required by ICH GCP guidelines, the PI will keep essential documents until at least 2 years after the last approval of a marketing application in an ICH region, and until there are no pending or contemplated marketing applications in an ICH region, or at least 2 years have elapsed since the formal discontinuation of clinical development of the IP. These documents should be retained for a longer period, however, if required by the applicable regulatory requirements or by an agreement with the Sponsor. The documents will be archived either in the MRCG at LSHTM Archive or at any other secure location as agreed upon with the Sponsor. It is the responsibility of the Sponsor to inform the PI/institution as to when these documents no longer need to be retained.

Following completion of the study, serum samples and nasal swabs collected during respiratory-related adverse events will be stored at an appropriate place in a designated freezer at the [REDACTED] [REDACTED] [REDACTED] until it is determined whether the samples are to be retained or destroyed under the direction of PATH. During the informed consent procedures, additional consent for the use of any serum remaining at the end of the trial and nasal swabs collected during respiratory-related adverse events for other ethically approved research will be sought from subjects' parents by the PI. Any such use must be with the consent/approval of PATH. When such additional consent has not been obtained the PI will destroy remaining serum and nasal swab samples based on the Sponsor's instructions (with proper audit documentation, reconciliation, and certification).

No data will be destroyed without the agreement of the Sponsor. The applicable records include source documents, site registration documents and reports, correspondence, ICFs, and notations of all contacts with the subject. The Sponsor will inform the PI in writing of the need for record retention and will notify the PI in writing when the trial-related records are no longer needed. Subjects' medical records and other original data will be archived in accordance with the local regulations or facilities of the investigational site.

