The subjects will be monitored daily at home by field workers for assessment of local and systemic reactogenicity during the 6 days after each study vaccine administration. Reactogenicity scoring will be reviewed by a research clinician (RC) prior to being entered into the OpenClinica database system.

Subjects will be monitored for adverse events (AEs) at each clinic visit through 9 months of age, and from booster vaccination through 4 weeks of follow up. For subjects who receive the booster vaccination at 9 (+1) months of age, monitoring for all unsolicited AEs will occur through the entire study period. For subjects who receive the booster vaccination at > 10 months of age, only monitoring for serious adverse events (SAEs) will occur from 10 months of age until booster vaccination. Monitoring for all unsolicited AEs will resume from when the booster vaccination is administered through the 4-week follow-up period.

AEs will be coded using the Medical Dictionary for Regulatory Activities (MedDRA) (version 21.0 or later) and assessed by the PI with regard to severity, relatedness, and duration. Any SAE ongoing at the time of the subject's EOS visit will be attempted to be followed until it is resolved, assessed as resolved with sequelae by the PI, or until last subject last visit (LSLV) in the trial (i.e. last subject completes V6). Any SAE deemed related to study vaccine that is ongoing at the time of LSLV will continue to be followed until it is resolved, assessed to be resolved with sequelae, or assessed to be stable/chronic. SAEs deemed not related to study vaccine that are unresolved at the time of LSLV will be classified as ongoing for the purposes of data lock but will continue to be followed by the investigator team or referred on, if appropriate, according to good practice in The Gambia.

To facilitate rigorous safety monitoring, data captured on CRFs at each visit will be entered into the OpenClinica database system within 3 business days from the date of the clinic visit. Home visit data (Day 1-6 following vaccination) will be entered in the OpenClinica database system within 3 days of the Day 6 home visit.

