5.6. Accountability and Disposal

Following vaccination, the vaccine vials/PFS will be labeled with the screening number of the subject to whom the vaccine has been administered using prepared stickers. The person who administered the vaccine and the time and date of vaccine administration will also be documented in an appropriate vaccine accountability log on the day of vaccination. All used vials/PFS without the needle will be stored in a dedicated space that is accessible only to the unblinded site personnel and the unblinded CRO monitor (and ultimately disposed of after completion of the study).

In case a vial/PFS of vaccine is broken or unusable, the unblinded site personnel will promptly inform the unblinded monitor and store the vial/PFS for accountability, following all safety precautions. In case a broken vial/PFS cannot be stored safely for accountability, appropriate discard and documentation will be followed after consultation with the unblinded monitor. Study product prepared but not administered to subjects, and all unused study product, will likewise be documented per drug accountability processes and discarded after the study is completed or terminated after notification by the CRO study drug monitor.

The designated unblinded site personnel will maintain a complete and accurate inventory of study vaccines received (including the quantity of vaccines received, date of receipt, condition at receipt, temperature noted during transit), those administered, and any broken or destroyed.

The unblinded CRO monitor will visit the site (including field sites) periodically throughout the trial to review and verify vaccine accountability records, as well as to ensure compliance with all trial procedures by the unblinded site personnel. After final vaccine accountability is completed by the unblinded CRO monitor, any used or unused vials/PFS of study vaccine will be destroyed at the site under the supervision of the unblinded site personnel after permission from the local regulatory authority has been obtained. Due to the need to maintain blinding, no vaccine accountability records will be sent to the Sponsor or included in the trial master file (TMF) until after database lock.

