7.4. Blinded and Unblinded Study Personnel

With the exception of the designated unblinded site personnel described below, all study site personnel, including the PI and the Sponsor, will remain blinded to subjects' treatment assignments. All CRO personnel, with the exception of the unblinded monitor, clinical supplies manager, an administrator and statistician for the DSMB (if required) will remain blinded to the treatment assignments. After the last subject completes V4, an independent CRO statistician (whose responsibilities are otherwise limited to supporting the DSMB) will be unblinded to conduct an interim analysis of immunogenicity objectives through end of V4. Study unblinding will be conducted and documented in accordance with relevant CRO standard operating procedures (SOPs). The Sponsor, Principal Investigator, site team and rest of the CRO personnel will continue to remain blinded to individual treatment assignments until all subjects complete Visit 6.

During conduct of the study, a limited number of unblinded site personnel will be responsible for preparing and administering study vaccines, performing vaccine accountability, and maintaining the security of the treatment assignments. The unblinded site personnel will not be involved in the safety assessment of the subjects, or in any other aspect of the study. All other site personnel, including those who perform the clinical evaluations (such as but not limited to assessment of medical history, vital signs assessment, and PE), will be blinded with respect to the identity of the vaccine administered to the subjects.

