13. STUDY MONITORING

Sponsor monitoring responsibilities will be provided by the CRO. A site initiation visit will be conducted prior to beginning the study, and monitoring will be during and at closeout of the study by the study monitor or designee. See Section 7.4 for a discussion of the roles of blinded and unblinded study monitors in this study.

During the course of the study, the monitor will visit the site (including field sites) at intervals to verify compliance to the protocol; completeness, accuracy, and consistency of the data and study vaccine accountability; adherence to protocol and regulatory obligations; and to ensure that conduct of the research follows GCP. The monitor should have access to subject medical records, study vaccine accountability and other study-related records needed to verify the entries on the CRFs.

The PI and the monitor will cooperate to ensure that any problems detected in the course of these monitoring visits, including OpenClinica database completion and query resolution, are resolved in a predefined time frame to be agreed in the Clinical Monitoring Plan.

To ensure the quality of clinical data for all subjects, a clinical data management review will be performed on subject data received by the CRO. During this review, subject data will be checked for consistency, omissions, and any apparent discrepancies. In addition, the data will be reviewed for adherence to the protocol and GCP. To resolve any questions arising from the clinical data management review process, data queries and/or site notifications will be sent to the site for resolution as soon as possible and within the time frame described in the Clinical Monitoring Plan; all queries must be resolved prior to database lock.

Essential documents must be filed in the site study file on an ongoing basis and be available for review by the Sponsor's contracted site monitor. Monitoring visits will be performed according to the Clinical Monitoring Plan.

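### Protocol 11.2.2 places vaccine accountability records in the blinded PI's Investigator Site File, against the blinding rules elsewhere, and the 5.6 embargo does not cover that file

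*Protocol*

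**What the plan says.** Protocol 11.2.2 gives the rule for the site's paperwork: "The PI will maintain an Investigator Site File, which will be used to file the IB, protocol, vaccine accountability records", together with correspondence and other study documents. The same paragraph makes this a duty during conduct and not only at archiving: "The PI will maintain, and store securely, complete, accurate and current study records throughout the study". Section 13 adds that "Essential documents must be filed in the site study file on an ongoing basis", and that they must be open to the Sponsor's contracted site monitor.

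On blinding, section 7.4 states that, apart from designated unblinded site staff, "all study site personnel, including the PI and the Sponsor, will remain blinded to subjects' treatment assignments". Section 3 has adverse events "assessed by the PI with regard to severity, relatedness, and duration".

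Section 5.6 recognises that accountability records threaten the blind. Giving the maintenance of blinding as its reason, it says that "no vaccine accountability records will be sent to the Sponsor or included in the trial master file (TMF) until after database lock". It also says that "the vaccine vials/PFS will be labeled with the screening number of the subject" who received the dose, and it limits access to the used vials and syringes to unblinded site personnel and the unblinded CRO monitor.

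**The concern.** One section tells a blinded person to hold, in a file that person maintains, records that another section withholds from other blinded parties because they could reveal treatment. The embargo names two recipients and leaves out the third place where the protocol says the records go.

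The PI is the person whose blind matters most for the safety endpoints. The PI assesses severity and relatedness of unsolicited events and SAEs, both within the primary safety endpoints (2.3.1). The PI also confirms reactogenicity events (9.2.1), has discretion, in consultation with the Sponsor, over further study vaccination when a window has been missed (7.2), and belongs to the Protocol Safety Review Team, whose reviews are to be blinded for every member (10.1). Section 7.5 treats unblinding of the PI as an emergency step for one child, with a stated rationale and a record. Routine filing of accountability records in the PI's file would offer a way round that control that leaves no record.

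**Working it through.** The plan gives no figure on this point, so the check sets the provisions side by side.

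**1. Who performs accountability and guards assignments?**
- Protocol 5.4: accountability procedures, cold-chain monitoring included, belong to the unblinded personnel.
- Protocol 5.6: labelled used vials and syringes are open only to unblinded site staff and the unblinded monitor, and that monitor verifies the accountability records.
- Protocol 7.1.2: the list of vaccine by randomization ID is kept where blinded staff cannot reach it.
- Protocol 7.4 and SAP 3.3: accountability and the security of assignments are tasks of the unblinded staff.

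These agree with one another. They cover who does the work, who handles the vials and who sees the allocation list. None says where the accountability paperwork sits at the site before database lock.

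**2. Where is the paperwork filed?**
Only 11.2.2 answers this, and it names the PI's Investigator Site File. It gives no restricted section and no date. Section 13 calls for ongoing filing; I take its site study file and the Investigator Site File to be the same thing, which the protocol does not state.

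**3. Does the embargo close the gap?**
Section 5.6 withholds the records from the Sponsor and the TMF until after database lock. The Investigator Site File is not named. Section 7.4 similarly bars blind-breaking monitor reports from the TMF before lock.

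**4. Do the records reveal allocation?**
The protocol treats them as able to, since blinding is its stated reason for the embargo. The exact linkage is partly inference. The screening number goes on the vial or syringe. The log is described as recording the administrator, date and time; vaccine and subject are not listed as log fields. The inventory does cover vaccines administered, the timing of study vaccination is entered on the CRF (7.1.2), and the three products come in different presentations: five-dose vial, single-dose vial and pre-filled syringe (5.1.3, 5.2.3, 5.3.3). A product-specific entry with a time could therefore be matched to a child's visit.

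**5. Could someone other than the PI keep the file?**
The abbreviation list defines PI as PI or designee. Nothing requires that designee to be unblinded. Section 7.4 keeps unblinded staff out of all other aspects of the study, so running the general site file is outside their stated role.

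Result: 11.2.2 is a stated rule that conflicts with steps 1 and 3.

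**The case against.** The strongest reply is that 11.2.2 comes under record archival, assigns a filing duty and grants no blinded person access to anything. A site that reads the whole protocol would restrict these records, because the operative sections put them in unblinded hands. Section 13 itself refers to 7.4 for the roles of blinded and unblinded monitors. Custody is also not knowledge here: under 7.5 a sealed set of randomization envelopes is kept at the site for the PI's emergency use.

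Much of this stands. A reader might infer from 11.2.2 that the PI can see the allocation. The documents do not support that, because the labelled vials and the vaccine list are restricted and the log's fields are not fully described. A reader might also infer that every child's assignment is exposed, but that assumes the breach that would have to be shown.

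The reply does not remove the conflict. The envelopes are sealed and their opening is documented; 11.2.2 sets no comparable control on the accountability records. The other sections show what was intended, but no other section says where this paperwork is kept before lock. If the TMF were read as including the site file, which the protocol does not say, 5.6 would forbid before lock what 11.2.2 calls for throughout the study, and the two would still need reconciling.

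**Conclusion.** The point holds as an internal inconsistency that carries a potential risk to the blind. The design itself, with unblinded staff, secure storage and an unblinded monitor, is sound. If 11.2.2 is followed as written, the PI could gain access to records that the protocol treats as unblinding. Blinded CRO monitors might as well, since section 13 opens the site file to the monitor and 7.4 gives blinded monitors responsibility for regulatory and audit readiness.

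The size cannot be stated. The documents show no breach and give no basis for estimating how far knowledge of the vaccine would shift relatedness judgements. A reader might try to size it from the most common vaccine-related event in VAC-056, vaccination-site swelling (0.3% PNEUMOSIL, 0.7% Synflorix, section 1.8.1). That does not work: swelling through Day 6 is solicited in this trial, and 9.2.3 excludes solicited events from relatedness judgement. Only swelling still present at Day 6 or starting later becomes an unsolicited event (9.2.1). The immunogenicity endpoints are less exposed, because laboratory staff running the assays stay blinded (12.5).

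The conclusion assumes that the accountability records carry enough to identify the vaccine given, as 5.6 implies, and that no site procedure outside these documents already separates them. The correction should be made because it costs little and protects the assessor on whom the safety endpoints depend.

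**What to change.** 1. In 11.2.2, remove vaccine accountability records from the general list. State that they are held in a separate restricted file kept by the unblinded site personnel, reviewed only by the unblinded monitor, and moved to the Investigator Site File only after database lock and unblinding of the site team.
2. In 5.6, add the Investigator Site File to the embargo sentence beside the Sponsor and the TMF.
3. In section 13, make the ongoing-filing sentence, and the monitor's access to the site file, subject to that embargo.

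The cost is wording in three protocol sections. The unblinded team, its secure storage and the unblinded monitor are already provided for, so no staff, data collection or analysis changes. If a site procedure already keeps these records apart, citing it in 11.2.2 would meet the first item.
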